--	--

Study Drug, Dosage, and Route of Administration:	
The sponsor (Palladio Biosciences, Inc.) will supply lixivaptan 50 mg capsules and matching placebo for use during the study. Throughout the study, participants will take 4 capsules BID to mask transitions from one study period to the next. All doses will be self-administered by participants orally at home with the exception of Visit 3 and any other study visit with scheduled sparse PK sampling, where in-clinic dosing may be warranted.
 
Part 1: During the Placebo Run-in Period, each participant will take 4 placebo capsules BID (twice daily, approximately 10 hours apart) for 1 week. During the Lixivaptan Titration Period, dosing will start at Level 1 (50 mg BID) and will be increased weekly minimally through Level 2 (100 mg BID) and maximally through Level 4 (200 mg BID) according to the dosing schedule shown in Table 1. At the 2 highest dose levels (Level 3 [150 mg BID] and Level 4 [200 mg BID]) where aquaretic effects may be problematic in certain participants, there will be an opportunity to reduce the evening (PM) dose to Level 3a (150 mg AM/100 mg PM) for those at Level 3 or Level 4a (200 mg AM/150 mg PM) for those at Level 4. Further dose reductions are allowable as shown in the Lixivaptan Titration Period (Part 1) — Lixivaptan Titration Flowchart. Throughout the study, participants will continue to take 4 capsules BID to mask transitions from one study period to the next.
 
Table 1. Dosing Levels during the Titration Period
 
  
 Dose Level	AM Dose	PM Dose	
   
 1*	50 mg	50 mg	
 
 2	100 mg	100 mg	
 
 3	150 mg	150 mg	
 
 3a**	150 mg	100 mg	
 
 4	200 mg	200 mg	
 
 4a***	200 mg	150 mg	
  
 
*Dose Level 1 is for initiation of treatment. **Participants having difficulty tolerating Dose Level 3 can drop back to 150 mg in the AM and 100 mg in the PM (Dose Level 3a: 150/100 mg). ***Participants having difficulty tolerating Dose Level 4 can drop back to 200 mg in the AM and 150 mg in the PM (Dose Level 4a: 200/150 mg).
 
Once tolerability is achieved, participants will remain on that dose for 1 additional week to confirm tolerability (Lixivaptan Titration Period (Part 1) — Lixivaptan Titration Flowchart). As the maximum duration of the Lixivaptan Titration Period is 6 weeks, participants who require a dose reduction at Week 6 as a result of emerging tolerability issues, will proceed to the double-blind period on the newly assigned (reduced) dose level without extension of the titration period. Participants who are unable to tolerate the minimum dose for entry into the Double-blind, Randomized Treatment Period (100 mg BID/ Level 2) will be discontinued from the study.
 
Participants who tolerate their optimized dose will then enter the Double-blind, Randomized Treatment Period during which time they will be randomized 2:1 (lixivaptan: placebo) to continue at the lixivaptan dose level achieved at the end of the Lixivaptan Titration Period or receive matching placebo capsules. During the Double-blind, Randomized Treatment Period, the dose may be adjusted downward at the Investigator’s discretion if needed
	Dose Level	AM Dose	PM Dose	1*	50 mg	50 mg	2	100 mg	100 mg	3	150 mg	150 mg	3a**	150 mg	100 mg	4	200 mg	200 mg	4a***	200 mg	150 mg

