--	--

[figure not shown]
	
Table 2. Dose Titration (Part 2) Based on Dose Level Achieved at End of Double-blind Randomized Treatment Period in Part 1 for Participants Assigned to Lixivaptan or Placebo in Part 1
 
  
 Dose Level in Part 1*	Week 1	Week 2	Week 3	Week 4	
   
 Level 1 100mg BID or Placebo	50mg BID	100mg BID			
 
 Level 2 150mg BID or Placebo	50mg BID	100mg BID	150mg BID		
 
 Level 3a 150/100mg (AM/PM) or Placebo	50mg BID	100mg BID	150/100mg (AM/PM)		
 
 Level 4 200mg BID or Placebo	50mg BID	100mg BID	150mg BID	200mg BID	
 
 Level 4a 200/150mg (AM/PM) or Placebo	50mg BID	100mg BID	150mg BID	200/150mg (AM/PM)	
  
 
*Participants whose dose was reduced to Level 1 (50 mg BID lixivaptan or placebo) during the double-blind phase as a result of tolerability issues or treatment-emergent AEs can continue on that dose during the open-label phase. These participants will initiate dosing with lixivaptan at 50mg BID and remain on that dose for 2 weeks during the Re-titration Period and initiate the open-label phase at that dose. Attempts will be made every 4 to 8 weeks to re-establish dosing at Level 2 (100 mg BID) during the open-label phase.
	Dose Level in Part 1*	Week 1	Week 2	Week 3	Week 4	Level 1 100mg BID or Placebo	50mg BID	100mg BID			Level 2 150mg BID or Placebo	50mg BID	100mg BID	150mg BID		Level 3a 150/100mg (AM/PM) or Placebo	50mg BID	100mg BID	150/100mg (AM/PM)		Level 4 200mg BID or Placebo	50mg BID	100mg BID	150mg BID	200mg BID	Level 4a 200/150mg (AM/PM) or Placebo	50mg BID	100mg BID	150mg BID	200/150mg (AM/PM)
Dose Level in Part 1*	Week 1	Week 2	Week 3	Week 4																											
Level 1 100mg BID or Placebo	50mg BID	100mg BID																													
Level 2 150mg BID or Placebo	50mg BID	100mg BID	150mg BID																												
Level 3a 150/100mg (AM/PM) or Placebo	50mg BID	100mg BID	150/100mg (AM/PM)																												
Level 4 200mg BID or Placebo	50mg BID	100mg BID	150mg BID	200mg BID																											

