Lixivaptan Re-Titration Period (Visits 26 to 29): For all participants, titration of lixivaptan will occur over a 2 to 4-week re-titration period and will start at a dose of 50 mg BID beginning at the conclusion of Visit 25. The dose will be increased at weekly intervals until the dose level from the end of the Double-blind, Randomized Treatment Period in Part 1 is achieved. In order to maintain blinding of the treatment assignment from Part 1, the dose level assignment for Part 2 will continue to be managed by the IRT. The dose-titration schedule for this part of the study is described in [Table 2](#). In the event of tolerability issues,

dosing may be decreased. **Note:** during the Re-titration Period of Part 2, all participants are re-titrated with lixivaptan to the last actual dose level if they had received lixivaptan during the Double-blind, Randomized Treatment Period, or, if they had received placebo during the Double-blind, Randomized Treatment Period, to the last inferred dose level (the dose level equal to the active dose level had the participant been randomized to the active arm). Re-titration will be performed by the IRT, and the site, participant, and sponsor maintain a blinded status to the prior treatment assignment in Part 1. If no adjustment is made to the inferred dose during the Double-Blind, Randomized Treatment Period, the last inferred dose for a participant randomized to placebo will be equal to the maximal tolerated lixivaptan dose established during the Titration Period in Part 1.

Maintenance Treatment Period (Visits 30 to 42): Following completion of the Lixivaptan Re-titration Period, participants will continue to receive lixivaptan in the Maintenance Treatment Period for 52 weeks at the same dose achieved at the end of the Re-titration Period in Part 2. If the participant's dose was decreased during the Lixivaptan Re-Titration Period, attempts will be made every 4 to 8 weeks to re-establish the previously achieved dose level (actual or inferred) at the end of the Double-blind, Randomized Treatment Period of Part 1. Visits will be performed every 4 weeks during this period. Assessments at each visit are detailed in the [Schedule of Procedures – Part 2](#).

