Treatment may still be restarted during or after these assessments are completed; any remaining serum creatinine assessments and the post-baseline MRI will not need to be completed if treatment is restarted during this period. If treatment is restarted, and the participant resumes study visits to Week 52 (completion of Visit 22 if in Part 1) or Week 104 (completion of Visit 42 if in Part 2), and has at least 1 scheduled Follow-up Period assessment for Part 1 or Part 2, respectively, then the eGFR assessments and MRI obtained during the period of study drug interruption will be considered as unscheduled and will not be included in the primary efficacy analysis for eGFR or the secondary efficacy analysis related to TKV. This procedure is designed to ensure that data for the primary and secondary endpoints are collected from all participants.

Participants with a study drug interruption 4 weeks or less in duration should resume study treatment at their last dispensed dose (or at a lower dose, if medically appropriate) without the need for stepwise dose re-establishment.

Participants with a prolonged study drug interruption (i.e., greater than 4 weeks in duration) equal to or less than 8 weeks), who are re-initiating treatment are required to re-establish their last tolerated dose over a 2-week interval. Re-initiation of treatment will begin with study drug at Level 2 for one week and will then be increased to the highest level the participant was receiving prior to the study drug interruption during the second week as described in [Table 6](#) (see pharmacy manual for further details related to study drug dispensing following a prolonged drug interruption.) The dose level assigned during Week 2 may be lowered based on Investigator discretion and clinical need. The IRT system will be used to manage re-establishment of dose.

Table 6. Dose Re-establishment Following a Prolonged (> 4-week) Study Drug Interruption

Last tolerated study drug dose level/ dose*	Week 1	Week 2**
Level 2/ 100mg BID	100mg BID	100mg BID
Level 3/ 150mg BID	100mg BID	150mg BID
Level 3a/ 150/100mg (AM/PM)	100mg BID	150/100mg (AM/PM)
Level 4/ 200mg BID	100mg BID	200mg BID
Level 4a/ 200/150mg (AM/PM)	100mg BID	200/150mg (AM/PM)

*Participants whose last tolerated dose level was 50mg BID prior to the prolonged treatment interruption, will re-initiate study drug dosing at Level 1/ 50mg BID.

**A lower dose level may be assigned at Week 2 if clinically indicated.

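### Two of the five row labels in Protocol Table 2 (Part 2 re-titration) give a level number a different dose from the table's own footnote, Table 1, Table 6 and SAP 3.3

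*Protocol*

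**What the plan says.** Table 2 (Protocol Synopsis, Study Drug, Dosage, and Route of Administration) gives the weekly steps for the Lixivaptan Re-titration Period. Its row key is the dose level from Part 1, and each row label combines a level number with a mg dose. The first two rows read "Level 1 100mg BID or Placebo" and "Level 2 150mg BID or Placebo". The remaining rows are Levels 3a, 4 and 4a.

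The footnote attached to that row key uses the level numbers differently. It refers to "Participants whose dose was reduced to Level 1 (50 mg BID lixivaptan or placebo) during the double-blind phase", and it asks for attempts "to re-establish dosing at Level 2 (100 mg BID) during the open-label phase".

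Other parts of the plan define the levels as follows:

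- Protocol Table 1 lists Levels 1, 2 and 3 as 50, 100 and 150 mg twice daily.
- Protocol 4.2.3, Table 6, has rows "Level 2/ 100mg BID" and "Level 3/ 150mg BID". Its footnote gives Level 1 as 50 mg BID.
- SAP 3.3 and SAP Table 1 repeat the Table 1 definitions.

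Protocol 3.1.2 and 6.6 state the Part 2 target as a dose level: the last actual level for participants who received lixivaptan, and the last inferred level for those who received placebo. Both sections refer to Table 2 for the schedule. Section 3.1.2 adds that "the dose level assignment for Part 2 will continue to be managed by the IRT".

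**The concern.** Within one table the same level number carries two doses. Level 1 is 100 mg BID in a row and 50 mg BID in the footnote. Level 2 is 150 mg BID in a row and 100 mg BID in the footnote.

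This matters because the plan carries the level, and not only a mg amount, from Part 1 into Part 2. A placebo participant took no lixivaptan in the double-blind period, so that participant's target exists only as an inferred level. Anyone who writes or checks the IRT specification from Table 2, using the level number as the key, could reach a different schedule from someone using the mg dose.

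Level numbers are also working terms elsewhere. Protocol Appendix 5 steps the dose down one level at a time until Level 1 is reached. SAP Section 9 tabulates participants by dose level during the maintenance period. Both need one meaning per level.

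**Working it through.** The plan gives no figure to reproduce here. The check is a row-by-row comparison of Table 2 with the other definitions.

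| Table 2 row label | Last weekly step in that row | Same level in the Table 2 footnote | Same level in Table 1 and SAP 3.3 | Same level in Table 6 | Label agrees? |
|---|---|---|---|---|---|
| Level 1, 100 mg BID | 100 mg BID (Week 2) | 50 mg BID | 50 mg BID | 50 mg BID (footnote) | No |
| Level 2, 150 mg BID | 150 mg BID (Week 3) | 100 mg BID | 100 mg BID | 100 mg BID | No |
| Level 3a, 150/100 mg | 150/100 mg (Week 3) | not mentioned | 150/100 mg | 150/100 mg | Yes |
| Level 4, 200 mg BID | 200 mg BID (Week 4) | not mentioned | 200 mg BID | 200 mg BID | Yes |
| Level 4a, 200/150 mg | 200/150 mg (Week 4) | not mentioned | 200/150 mg | 200/150 mg | Yes |

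**Labels.** Two of five conflict and three agree. Table 1 has six levels (1, 2, 3, 3a, 4, 4a). Level 3 is the only one with no row under its label in Table 2, although its dose of 150 mg BID has a row, labelled Level 2.

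**Mg doses.** In five of five rows the last weekly step equals the mg dose printed in the label. Five of the six Table 1 doses have a row. The sixth, 50 mg BID, is handled by the footnote. Read by mg, the table is one consistent schedule.

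**What a label-only reading would give:**

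- Level 2, which is 100 mg BID in Tables 1 and 6, leads to the 150 mg BID row. The daily dose would be 2 × 150 = 300 mg instead of 2 × 100 = 200 mg, a ratio of 300/200 = 1.5. There would be three weekly steps instead of two.
- Level 3 leads to no row.
- Level 1, which is 50 mg BID elsewhere, leads to a row that rises to 100 mg BID in Week 2: 2 × 100 = 200 mg/day instead of 2 × 50 = 100 mg/day. The footnote covers these participants separately and keeps them at 50 mg BID for two weeks, so the table itself settles this case, but Level 1 then has two schedules in one table.

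**Is this an artefact or superseded text?** The rows are complete and legible in the current protocol body. The same labels appear in the Version 2.0 summary of changes, so damage in text extraction is unlikely. The Version 3.0 summary records an edit to this table's footnote, and the row labels remain in the current version.

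**The case against.** The strongest reply is that nobody need be misled. Every row prints its mg dose beside the level number, and the steps end at that dose. A reader who looks for Level 2 as 100 mg BID and arrives at a row marked 150 mg BID sees the mismatch at once. The text that introduces the table says that everyone restarts at Level 1 with 50 mg BID, and the footnote repeats the usual definitions. Sites do not choose a row, because the IRT assigns the level. The 1.5-fold figure arises only if the printed mg dose is ignored.

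Most of this stands, and it limits the weight of the point. The mg schedule is coherent and no dispensing error has been shown. It does not remove the contradiction. The text that sends the reader to Table 2 speaks of dose levels, and the table's title and row key do the same. Reliance on the IRT moves the question to a specification that is not in the documents, and Table 2 is the protocol source for that specification.

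Practical reach is also small. SAP Section 12 records that the trial was terminated early with 5 participants randomized, all of whom stopped in Part 1. That lowers the urgency for this trial. It does not make the table consistent, and the table could be carried into later use.

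**Conclusion.** The concern holds. Two of the five row labels in Table 2 contradict the table's own footnote, Protocol Tables 1 and 6, and SAP 3.3, and one of the six Table 1 levels has no row under its label. The possible consequence is confined to a reading by level number: 300 versus 200 mg/day and three versus two weeks for Level 2, and no schedule for Level 3. These figures describe what the labels would imply, not doses known to have been assigned.

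The conclusion rests on the text of the two documents alone. Whether the IRT was keyed on level number or on mg cannot be determined from them. No endpoint, significance level, power or sample size is affected. This is an internal contradiction in a dosing table that should be corrected.

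**What to change.** Reconcile the Table 2 row labels with the Table 2 footnote, Protocol Tables 1 and 6, and SAP Table 1, so that each level number has exactly one dose throughout and each level that can be carried into Part 2 has a row or an explicit footnote. Which dose belongs to which level is for the sponsor to settle; no position is taken here.

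Then check the level-to-dose mapping in the IRT specification, including the inferred levels for placebo participants, against the reconciled table. Do this before anyone enters Part 2 under this protocol or any later protocol that reuses the table. Confirm that the dose-level tabulations in SAP Section 9 use the same mapping.

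The cost is a label correction in one protocol table and one specification check. No analysis changes.

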1 INTRODUCTION

1.1 Background

Lixivaptan (also known as VPA985, BIIB030, and CL 347,985) is a potent, non-peptide selective antagonist for the vasopressin V₂ receptor, which is expressed primarily in the collecting duct of the nephron (Chan et al, 1998). Lixivaptan antagonizes the effects of vasopressin that are mediated by the V₂ receptor, resulting in the pharmacologic effect of increased free water excretion, thus decreasing urine osmolality (U_{osm}), increasing urine flow, and increasing serum osmolality as well as restoring normal levels of intracellular cyclic adenosine 3',5'-monophosphate (cAMP) (Chebib, 2015).

The sponsor (Palladio Biosciences, Inc.) is currently developing lixivaptan for the treatment of autosomal dominant polycystic kidney disease (ADPKD). Lixivaptan had previously been under development for the treatment of symptomatic hypervolemic and euvoletic hyponatremia associated with heart failure and syndrome of inappropriate anti-diuretic hormone secretion.

Additional background information for lixivaptan can be found in the Lixivaptan Investigator's Brochure (IB).

1.2 Overview of ADPKD

Definition

ADPKD is a hereditary kidney disorder characterized by cyst formation and progressive enlargement in the kidney, liver, and other organs. It results from loss-of-function mutations in either of 2 genes (*pkd1* and *pkd2*), encoding transmembrane proteins polycystin 1 (PC1) and polycystin 2 (PC2), respectively.

In the kidney, loss-of-function mutations in *pkd1* or *pkd2* disrupt the normal differentiated phenotype of the renal tubular epithelium. These mutations lead to elevated intracellular levels of cAMP, which in turn results in increased cellular division and apoptosis, a loss of mitotic polarity, a disruption of the normal differentiated cellular phenotype, cyst formation, and fluid secretion into kidney cysts (Antignac et al, 2015). The progressive development and growth of numerous bilateral kidney cysts results in fibrosis, kidney architectural derangement, and destruction of normal kidney tissue. Disease progression is characterized by urine concentration defects, hypertension, acute and chronic pain, kidney stones, haematuria, cyst and urinary tract infections, and, most importantly, kidney function loss and kidney failure (Antignac et al, 2015, Chapman et al, 2015).

The most frequent extrarenal manifestation of ADPKD is polycystic liver disease, which is typically associated with increased kidney volume, older age, and female sex. Liver cysts are usually asymptomatic, and the liver chemistry is normal. However, in some cases the increased liver volume may lead to hepatomegaly as a result of the continuous cyst enlargement (Hogan et al, 2015). This may cause symptoms of extrinsic compression, such as abdominal pain, early satiety, and obstruction of the hepatic veins or bile duct. Moreover, liver cyst infections may cause fever, right upper abdominal pain, and/or possible elevated CA19.9 and alkaline phosphatase levels.

Epithelial cells derived from human ADPKD cysts generate elevated intracellular levels of cAMP in response to vasopressin, which in turn promotes cell proliferation and electrolyte secretion (Belibi et al, 2004). Increased fluid secretion into cysts is due to vasopressin-induced transepithelial secretion of chloride. Patients with ADPKD also have elevated plasma concentrations of vasopressin or an exaggerated vasopressin response to sodium challenge as compared to normal individuals (Torres, 2005). Pharmacological interventions aimed at inhibiting vasopressin signalling are, therefore, expected to restore normal cellular function and provide a disease-modifying effect on disease progression in ADPKD.

1.3 Overview of Available Therapies for ADPKD

Demonstration of the utility of vasopressin V₂ receptor antagonists for the treatment of ADPKD is provided by the experience with tolvaptan. Results from the TEMPO 3:4 Phase 3 trial showed that tolvaptan slowed the progression of kidney enlargement and delayed the worsening of kidney function (Torres et al, 2012). The study also established suppression of urine osmolality to <250 mOsm/kg as a predictive pharmacodynamic marker of clinical efficacy for a vasopressin V₂ antagonist for the treatment of ADPKD (Devuyst et al, 2017). Subsequently, the REPRISE Phase 3 study with tolvaptan demonstrated that the efficacy of vasopressin V₂ receptor antagonism is maintained in patients with later stage ADPKD (Torres et al, 2017).

The European Medicines Agency granted a positive opinion for tolvaptan (JINARC[®]) in 2015 to slow the progression of cyst development and failing kidney function in adult patients with ADPKD with normal to moderately-reduced kidney function who have rapidly progressing ADPKD. The Committee for Medicinal Products for Human Use recommended additional monitoring of the risk of liver damage with tolvaptan. Similar approvals were granted in Japan, Canada, and Australia/New Zealand.

In April 2018, tolvaptan (JYNARQUE[®]) was approved in the United States (US) to slow kidney function decline in adults at risk of rapidly progressing ADPKD. However, because of the risk of serious liver injury, Jynarque is only available through a restricted distribution program under a Risk Evaluation and Mitigation Strategy.

1.4 Rationale for Lixivaptan Therapy for ADPKD

Given that elevated kidney cAMP plays a pivotal role in the complex phenotypical manifestation of ADPKD (Belibi et al, 2004), and that vasopressin is the principal agonist pathway leading to the formation of cAMP in kidney tubule cells, it has been suggested that therapeutic interventions aimed at counterbalancing the effect of vasopressin and/or normalizing intracellular levels of cAMP may be effective in delaying disease progression in ADPKD (Torres, 2005). This hypothesis was confirmed by genetic experiments in mutated rats with no circulating serum vasopressin (Brattleboro rats). When these rats were crossed with rats harboring a PKD mutation, their offspring did not develop cysts (Wang et al, 2008), thus demonstrating that an intact vasopressin signaling pathway is a necessary requirement for the development of cystic disease. In addition, vasopressin receptor antagonists, including mozavaptan and tolvaptan, (Gattone et al, 2003 and Wang et al, 2005) have proved efficacious in normalizing kidney cAMP levels and correcting disease manifestations in preclinical rodent models of ADPKD. In ADPKD patients, elevated levels of circulating

copeptin, a marker for serum vasopressin concentration, are associated with faster disease progression (Boertien et al, 2012).

Further, definitive evidence in favor of the utility of vasopressin antagonism as a therapeutic approach for ADPKD is derived from tolvaptan, like lixivaptan a non-peptide vasopressin V₂ receptor antagonist in the drug class of vaptans. In Europe, tolvaptan (JINARC[®]) is approved to slow the progression of cyst development and kidney insufficiency of ADPKD in adults with CKD stage 1 to 3 at initiation of treatment with evidence of rapidly progressing disease. Approval was granted based on the findings from the pivotal Phase 3 trial TEMPO 3:4. The trial randomized 1445 patients with ADPKD with a total kidney volume of ≥ 750 mL and an estimated creatinine clearance of ≥ 60 mL/min to tolvaptan or placebo. Over a 3-year period, tolvaptan delayed the worsening of kidney function, a therapeutic effect that was subsequently found to have disease-modifying properties and slowed the progression of kidney enlargement (Torres et al, 2012 and 2017a). Importantly, the TEMPO 3:4 trial also demonstrated that, in patients receiving tolvaptan, there was a strong, inverse relationship between the magnitude of the aquaretic response, measured by decrease in urinary osmolality, and the loss of kidney function during the study (Devuyst et al, 2017). Because complete vasopressin suppression is ensured if urinary osmolality is lowered to < 250 mOsm/kg, these findings strongly suggest that achieving urinary osmolality reduction below this target threshold can be considered a predictive biomarker of clinical efficacy of vasopressin antagonists for the treatment of ADPKD (Devuyst et al, 2017).

More recently, the results of REPRISE, a second pivotal Phase 3 trial with tolvaptan for the treatment of ADPKD, were published (Torres et al, 2017). This trial randomized 1370 patients with later stage ADPKD, which was defined as having a baseline estimated glomerular filtration rate (eGFR) of < 65 mL/min for patients in the 18-55 age group or < 45 mL/min for patients in the 56-65 age group, to tolvaptan or placebo. Over a 12-month period, tolvaptan delayed the eGFR decline, a surrogate for worsening kidney function, with a magnitude of effect that was comparable to the one seen in the TEMPO 3:4 study (35%; $p < 0.0001$). Taken together, the results of these two studies demonstrate that the efficacy of vasopressin antagonism is maintained across multiple time periods and stages of disease.

The evidence supporting the potential utility of lixivaptan for the treatment of ADPKD is provided by experiments in animal models of polycystic kidney disease (PKD) and by the clinical effect of lixivaptan on urine osmolality, a pharmacodynamic biomarker of effective vasopressin antagonism that is correlated with efficacy in ADPKD, as discussed below.

Lixivaptan ameliorates disease manifestations in animal models of PKD

Lixivaptan was tested in rat and mouse animal models of PKD.

The PCK rat, an orthologous model of human PKD caused by a splicing mutation in the *pkhdl1* gene, is one of the best-studied models in the field of PKD research because it is characterized by a phenotype that is highly reminiscent of the human disease. Compared to control animals, PCK rats treated with lixivaptan showed a marked protective effect on the development of kidney disease manifestations, including reduced cystic burden, reduced kidney volume increase, and delayed kidney function decline. These beneficial effects were accompanied by a reduction in kidney cAMP levels, as expected (Wang et al, 2019).

The Pkd1^{RC/RC} mouse is a hypomorphic genetic model which closely mimics human ADPKD with slowly progressive PKD. Compared to control animals, Pkd1^{RC/RC} mice treated with lixivaptan showed a significant reduction in kidney weight, cyst volume, and fibrosis volume (Di Mise et al, 2021). The magnitude of efficacy observed with lixivaptan in the RC/RC mouse model is comparable to historical experiments conducted with tolvaptan (Hopp et al, 2015).

Additional background information on the effect of lixivaptan in the PCK rat and Pkd1^{RC/RC} mouse can be found in the IB.

Lixivaptan causes sustained suppression of urine osmolality to levels that are associated with therapeutic efficacy in ADPKD

The expectation about the efficacy of lixivaptan in ADPKD is supported by the observed clinical effects of lixivaptan on the pharmacodynamic biomarker of urinary osmolality. Clinical studies conducted with lixivaptan in healthy participants, ADPKD patients, and various other patient populations (patients with hypervolemic and euvolemic hyponatremia and patients with ESRD) demonstrated that treatment with lixivaptan readily suppresses urinary osmolality to levels below the target threshold of 250 mOsm/kg, irrespective of the specific patient population tested. Importantly, the magnitude of the effect observed with lixivaptan was comparable to the effect observed with tolvaptan in the same patient populations. In addition, like tolvaptan, treatment with lixivaptan was associated with a rapid-onset and fully reversible increase in serum creatinine. Taken together, these results suggest that treatment with lixivaptan can inhibit vasopressin receptor signaling to the extent necessary to observe clinical efficacy of a vasopressin antagonist for the treatment of ADPKD (Devuyst et al, 2017).

Additional background information on the effect of lixivaptan on urine osmolality can be found in the IB.

Lixivaptan as an alternative to tolvaptan with potentially less risk of liver toxicity

While tolvaptan has been approved in many territories to slow the progression of kidney function deterioration in patients with ADPKD, drug-induced liver injury (DILI) occurs in a certain percentage of patients taking tolvaptan. Acute liver failure requiring liver transplantation has also been reported (Endo et al, 2019). Patients on tolvaptan require frequent testing of liver chemistry and discontinuation of the drug when the test results are elevated in order to prevent serious outcomes.

DILI modeling using DILIsymTM, a Quantitative Systems Pharmacology model of drug-induced liver injury, has allowed for the assessment of potential abnormal liver chemistry tests prior to conducting large clinical trials (Woodhead et al, 2017a). DILIsym integrates physiologically based pharmacokinetic (PBPK) and *in vitro* toxicity data of parent compound and its active metabolites. Specific *in vitro* data incorporated into the model includes drug induced bile acid transporter inhibition, mitochondrial dysfunction, and oxidative stress, all of which have been identified as putative cellular mechanisms for DILI.

DILIsym was employed to model tolvaptan-mediated liver injury and was able to successfully recapitulate the observed toxicity (Woodhead et al, 2017b). The frequency of

predicted ALT elevations following simulated 90/30 mg split daily dosing, was 7.9% compared with clinical observations of 4.4-5.6% in ADPKD trials. The simulations also demonstrated that the *in vivo* hepatic exposure to tolvaptan and its main metabolite, DM-4103, combined with alterations in bile acid disposition and inhibition of mitochondrial respiration were sufficient to account for the initiation of tolvaptan-mediated liver toxicity.

This same platform was used to evaluate the potential of lixivaptan to cause liver toxicity (Woodhead et al, 2020). *In vitro* data relating to reactive oxygen species formation, mitochondrial toxicity, and bile acid transporter inhibition for lixivaptan and its major metabolites (WAY-138451, WAY-141624, and WAY-138758) were collected in parallel with tolvaptan as a positive control. Using these data, lixivaptan and its metabolites were represented in DILIsym. Proposed ADPKD treatment dosing regimens were simulated and the predicted potential for liver enzyme elevations was compared to that previously determined for tolvaptan in DILIsym. Results showed that lixivaptan was not predicted to cause liver enzyme elevations in a simulated human population which included variability in toxicity susceptibility and pharmacokinetics, while tolvaptan was correctly predicted to cause rare liver enzyme elevations in a similar population (Table 5).

Additional information regarding the DILIsym evaluation of lixivaptan can be found in the IB.

Table 5. DILIsym Simulations of Lixivaptan and Tolvaptan

Drug	Dose, Duration	Clinical ALT >3 x ULN	Simulated ALT >3 x ULN, n/N
Lixivaptan	200/100 mg q AM/PM, 12 weeks	UNK*	0/285
Tolvaptan**	90/30 mg q AM/PM, 24 weeks	4.4%	18/229 7.86%

*UNK = Unknown; data to be acquired in Phase 3

**Source: Woodhead et al, 2017b

